## **COST BENEFIT OF PROJECT**

Our hypothesis is that along with improved patient satisfaction and improved waiting times for outpatient appointment, there will be cost savings derived from the One Stop Vein Clinic. On average, 1,000 patients are treated every year in the Imperial College NHS Trust and the cost of an outpatient attendance is approximately £93. Savings could be made if patients are seen and treated at their first appointment rather than having to attend another two

appointments.

The potential cost saving is estimated to be in the order of £186,000 annually (£93 x 1,000 X 2).

#### **Estimated societal costs.**

Data will be collected on time off from work and carer's duties (child/relative/friend). Additionally, data on income, cost of attending clinic and impact on family and colleagues will be assessed to estimate the societal cost of the two pathways.

#### **ETHICAL ARRANGEMENTS**

The Chief Investigator has obtained approval from the National Research Ethics Service (NRES) Committee (**REC Ref.: 14/LO/1295**).

Patients will be screened and patients thought eligible will be sent an information pack with information about the trial and varicose veins and its treatments. They will be invited to the clinic and would be asked to confirm their consent by providing a written consent prior to participating in the trial. The National Health Service (NHS) Trust Research and Development approval will also be sought prior to starting the trial.

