## **METHODS**

GP referrals will be screened and patients meeting the inclusion criteria will be invited to take part in the trial.

They will be sent an information pack containing:

- Information leaflet about the trial
- Information about varicose veins, their treatments and a telephone number as a helpline
- The Aberdeen Varicose Vein Questionnaire (AVVQ), the Chronic Venous Disease Quality of Life Questionnaire (CIVIQ) and EuroQoL's quality of life questionnaire (EQ-5D)
- Consent form to participate in the study

Patients agreeing to be part of the trial will be consented and randomised either to:

- The One Stop Vein Clinic (offering same day diagnosis and treatment);  
or
- The normal care pathway

Once patients indicate their consent to participate, their General Practitioners (GP) will be sent a letter informing them of the patient's participation in this study.

Patients declining to partake in the randomised part of the study, but agreeable to complete study questionnaires while continuing down the normal care pathway, will also be consented. Further information will be provided to them when they attend for their clinic appointment and the consenting process will take place when they attend for their subsequent procedure

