### **One Stop Vein Clinic Pathway**

Patients attending the One Stop Vein Clinic will be reviewed by the Vascular Surgeon, who will confirm the patient's consent in the trial, then assess the degree of venous disease and fill in the Clinical-Etiology-Anatomy-Pathophysiology (CEAP) classification and Varicose Clinical Severity Score (VCSS). If the patient's symptoms are deemed secondary to venous disease, they will be sent to have a Duplex scan to confirm the presence of the venous disease. The results will be reviewed by the Vascular Surgeons, and if the patients are suitable for endovenous ablation +/- avulsions or UGFS, they will be informed of the findings of the scan and proposed treatment. If they are happy to go ahead with the proposed intervention, they will be consented and transferred to the waiting area to wait for their intervention. If, however, they decline same day treatment, they will be put onto the conventional care pathway.

Another Vascular Surgeon will be carrying out the interventions in an 'office-based' environment under local anaesthetic. Once done, the patients will be asked to fill the Picker patient experience questionnaire. They will subsequently be discharged, similar to current practice, and will be given a diary card to fill for when they return to their normal activities

and work.

Three (3) months post-operatively, they will be asked to fill the AVVQ, CIVIQ, EQ-5D and Picker patient experience questionnaires once more. This will be done by sending them the questionnaires by post.

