### **CONSENT**

As part of the consenting process, patients will be given three options.

1. Patients wishing to attend the One Stop Vein Clinic and participate in the study will be asked to indicate their consent by signing a consent form and filling in a reply slip. Patients will be randomised either to the One Stop Vein Clinic group or to the Normal Care Pathway (NCP) group.

2. Patients not wishing to attend the One Stop Vein Clinic and participate in the study will be asked to indicate this by filling in a reply slip. They will instead attend the normal care pathway. They will, however, be asked, if agreeable to complete the QoL and Picker patient experience forms.

3. Patients declining either the trial or simple service evaluation will be offered the NCP.

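### The protocol gives two consent sequences, and only the One Stop arm has a written clinic consent check, so entry or retention could depend on the allocated arm

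*Protocol*

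**What the plan says.** Several places in the protocol deal with when a patient consents.

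- **Methods.** Patients who pass screening of the GP letter are sent a pack that includes a "Consent form to participate in the study". The next step reads "Patients agreeing to be part of the trial will be consented and randomised either to" one of the two pathways.
- **Consent (option 1).** Patients who want to take part are "asked to indicate their consent by signing a consent form and filling in a reply slip. Patients will be randomised" to One Stop or to the normal care pathway.
- **Ethical Arrangements.** After the pack is sent, patients are "invited to the clinic and would be asked to confirm their consent by providing a written consent prior to participating in the trial". No earlier signed form is mentioned.
- **One Stop Vein Clinic Pathway.** The patient is seen at that clinic by the vascular surgeon, "who will confirm the patient's consent in the trial", before clinical assessment, scan and treatment.
- **The Normal Care Pathway.** The outpatient visit, scan, second visit, procedure and questionnaires are described. No trial consent step appears.
- **Inclusion and Exclusion Criteria.** Withdrawal of consent is listed among the exclusions.
- **Regulatory issues, Consent.** Signed consent is required after a full explanation and time to consider. Its timing relative to randomisation is not given.

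**The concern.** The moment at which a person becomes a trial participant is a protocol matter, and this protocol states it in two ways. If the signature that admits a patient is taken at a clinic that only one arm attends, the patient can already know the allocation when deciding whether to sign. The trial population would then be formed partly after randomisation.

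The pathways cannot be hidden from patients, and the Background reports that 90% of surveyed patients were agreeable to a one-stop clinic. A reaction to the allocation is therefore foreseeable. A consent check written for one arm only, together with an exclusion criterion that could be applied after allocation, gives that reaction a route into the comparison. The QALY and patient-satisfaction comparisons would then lose some of the protection that randomisation is meant to give.

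**Working it through.** No arithmetic applies. The check sets the sections side by side.

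**1. Order of signature and allocation.** Methods has consent and then randomisation. The Consent section has a signed form and reply slip and then randomisation. These two agree. Ethical Arrangements has the pack, then the clinic, then written consent as the condition for participating. The act that makes someone a participant is therefore placed at a different point.

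**2. Does the clinic visit come after allocation?** Ethical Arrangements does not say. The inference runs as follows.
- The only clinics described are the One Stop clinic and the normal-pathway outpatient clinic.
- No common visit before randomisation is described anywhere.
- One Stop patients are assessed, scanned and treated on the day of that visit, so their allocation must be settled before they attend.
- Hence a signature given at the clinic follows allocation, at least in One Stop, and in both arms if *the clinic* means whichever clinic the patient was allocated to.

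The flow chart does not strengthen this. Its boxes come through in scrambled order, so no sequence can be read from it.

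**3. Are the arms treated alike?** Among randomised patients, One Stop has a stated clinic consent check and the normal pathway has none. The other on-site trial consent, taken at the procedure under Methods, is for patients who declined randomisation and does not fill the gap.

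**4. What happens to a patient who does not confirm?** The protocol does not say. The regulatory Consent section keeps patients in follow-up and analysis when the clinician gives an alternative treatment. It does not say the same for patients who fail to re-affirm consent. Because withdrawn consent is listed as an exclusion, such a patient could be treated as never eligible.

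**5. Size and direction.** The documents give no rate of non-confirmation and nothing on how such patients would differ from the rest. Even the direction depends on the reading:
- If only the One Stop check operates, any loss at this step falls in One Stop.
- If the Ethical Arrangements sentence governs both arms, loss could occur in either, and disappointment would make it more likely in the normal pathway.

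A numerical estimate would have to assume the rate, the difference and the arm, so none is offered.

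**The case against.** The strongest reply is that the operative sections agree with each other and that Ethical Arrangements is only a brief summary. It says patients *confirm* consent, which presupposes consent already given, and the One Stop section uses the same verb. Read together, the patient signs, is randomised, and has consent re-affirmed at the clinic, so no one is randomised without prior written consent. The normal-pathway section mainly describes usual care, and its silence contradicts nothing, since Methods and Consent already cover both arms. Nor does the One Stop section say that a patient who fails to confirm leaves the analysis.

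Much of this stands. Re-affirmation is a fair reading of the One Stop section and a possible one of Ethical Arrangements. It does not fully clear the latter, where confirming is done by giving a written consent and that act comes before participation. It also leaves the check written for one arm only and the exclusion for withdrawn consent in place.

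A reader might go further and infer that patients will in fact be randomised and told their arm before signing anything. The documents do not support that: no section says so, and two say the opposite. Nor do they say that the signed form comes back by post. That is suggested by the mailed pack and the reply slip, but it is not stated.

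**Conclusion.** The concern holds as an inconsistency in the protocol with a possible, unquantified consequence. Two consent sequences are stated. The literal reading of one puts written consent after allocation, and a clinic consent check is written for one randomised arm only. With withdrawn consent listed as an exclusion, entry or retention could depend on the arm.

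This rests on two assumptions: that there is no common clinic visit before randomisation, since none is described, and that patients know their pathway when they attend. It does not establish that bias will occur, in which arm, or how large it would be. The point merits correction because the gap is easy to close and concerns who is counted in the randomised comparison.

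**What to change.** Reconcile Methods, One Stop Vein Clinic Pathway, The Normal Care Pathway, Inclusion and Exclusion Criteria, Consent, and Ethical Arrangements so that they give one sequence:

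1. The signed consent form is received before randomisation, however it is returned, and after the explanation that the regulatory Consent section requires.
2. Any consent step at a clinic is described as a re-affirmation and is done identically at the first clinic visit in both arms. Otherwise it is removed from the One Stop section.
3. Every randomised patient counts as a participant in the allocated arm from randomisation. Later withdrawals of consent are reported by arm and are not treated as ineligibility. The withdrawal item in the exclusion list is reworded to match.

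The cost is a short wording amendment, with no extra visits or data collection.

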#### **DATA HANDLING & DISSEMINATION OF RESULTS**

All patient data will be anonymised and stored on a password protected access database under the guidelines of the Data Protection Act 1998. Patient records will be kept on paper in the form of the diary card questionnaires and clinical scoring sheets, which will be kept in a locked filing cabinet at Charing Cross Hospital for 10 years in accordance with the Imperial College Trust Policy.

#### **DISSEMINATION OF RESULTS**

##### **For Patients/Public**

We will produce a short, easy to understand summary of our research findings that will be available from our website or that can be sent to interested parties. There will also be significant patient and public engagement through new and existing conferences and open days.

##### **For academics**

Knowledge will be disseminated through peer-reviewed scientific publications in leading international, high impact journals (e.g. Lancet, BMJ, Annals of Surgery; Health Affairs; or relevant open access journals, where possible and appropriate), and presentations at local, national and international conferences. A balanced approach will be adopted to maximise the impact and output of the studies. In line with all research funded by the NIHR, we will produce a full and complete account of the research ensuring that the work is reported fully and publicly available.

##### **For Health Managers**

We will disseminate findings to a specialist audience, including health care commissioners, policy makers, Department of Health, and specialist providers. The study results will be presented to healthcare commissioners and policy makers at appropriate meetings and publications. A summary of results, in language appropriate for lay persons, will be sent to all relevant patient groups. We will provide details of simulations on a web based platform to facilitate the adoption of our model and methodology in other fields. The dissemination strategy for our findings will be aimed at reaching the largest possible stakeholder audiences.

#### **CRITERIA FOR ELECTIVELY STOPPING THE TRIAL OR OTHER RESEARCH PREMATURELY**

The trial may be stopped prematurely due to loss of equipoise or any major adverse effect as a result of treatment in any of the treatment arms.

##### **Adverse events**

No significant adverse events are expected.

**Adverse Event (AE):** any untoward medical occurrence in a patient or clinical study subject.

**Serious Adverse Event (SAE):** any untoward and unexpected medical occurrence or effect that:

- **Results in death**
- **Is life-threatening** – refers to an event in which the subject was at risk of death at the time of the event; it does not refer to an event which hypothetically might have caused death if it were more severe
- **Requires hospitalisation, or prolongation of existing inpatients' hospitalisation**
- **Results in persistent or significant disability or incapacity**
- **Is a congenital anomaly or birth defect**

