#### *Adverse Events (AE)*

All such events, whether expected or not, should be recorded.

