#### *Serious Adverse Events (SAE)*

An SAE form should be completed and faxed to the Chief Investigator within 24 hours.

All SAEs should be reported to the Sponsor where in the opinion of the Chief Investigator, the event was:

- 'related', ie resulted from the administration of any of the research procedures; and
- 'unexpected', ie an event that is not listed in the protocol as an expected occurrence

Reports of related and unexpected SAEs should be submitted within 15 days of the Chief Investigator becoming aware of the event, using the NRES SAE form for non-IMP studies.

Local investigators should report any SAEs as required by their Local Research Ethics Committee, Sponsor and/or Research & Development Office.

In the event of any harm to participants in the trial, Imperial College holds Public Liability ("negligent harm") and Clinical Trial ("non-negligent harm") insurance policies, which apply to this trial. All issues will be reviewed by the TMC (AHD/CB/KD/RB), [name] (Professor of Vascular Surgery) will be available as an independent advisor.

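### The SAE definition requires an event to be unexpected, which conflicts with the later sponsor-reporting test and can exempt a serious event judged expected from the 24-hour form

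*Protocol*

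**What the plan says.** Four parts of the protocol bear on this.

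- **Adverse events.** The section opens with the statement "No significant adverse events are expected". It defines an adverse event (AE) as "any untoward medical occurrence in a patient or clinical study subject", with no condition on expectedness. It defines an SAE as "any untoward and unexpected medical occurrence or effect that" leads to death, threat to life, hospitalisation, lasting disability or a birth defect.
- **Reporting procedures.** All adverse events go to the trial management committee through the Chief Investigator, and into the trust's incident system. No time limit is given.
- **Adverse Events (AE).** "All such events, whether expected or not, should be recorded". Again no time limit is given.
- **Serious Adverse Events (SAE).** "An SAE form should be completed and faxed to the Chief Investigator within 24 hours". The section then sets the sponsor rule: "All SAEs should be reported to the Sponsor where in the opinion of the Chief Investigator, the event was" related and unexpected. It explains unexpected as "an event that is not listed in the protocol as an expected occurrence". Reports of related and unexpected SAEs are due within 15 days of the Chief Investigator becoming aware of the event.

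**The concern.** Whether an event is serious depends on its outcome. Whether it was expected is a different question, normally asked afterwards to decide who else must be told. The Adverse events section merges the two, while the Serious Adverse Events (SAE) section keeps them apart.

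What is at stake is the fast internal report. The 24-hour form is the only reporting step with a limit measured in hours, and it is tied to the SAE label. If a complication that leads to hospital admission is a recognised consequence of vein treatment, a treating clinician could reasonably call it expected. On the wording of the definition, that clinician need not complete the form. Whether the Chief Investigator hears within a day would then turn on the reporter's private view of what was expected.

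**Working it through.** No arithmetic applies. The check sets the sections side by side.

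**Step 1: is expectedness part of the SAE definition?** Yes. The AE definition has no such condition. The SAE definition, in the same section, adds it through the word 'unexpected'. An event must therefore be untoward, unexpected and serious in outcome to qualify.

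**Step 2: does the later section agree?** No. It starts from all SAEs and keeps for the sponsor those that are both related and unexpected. If every SAE is unexpected by definition, the second condition removes nothing. It has a purpose only if an SAE may be expected. The two sections cannot both be meant as written.

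**Step 3: which meaning of 'unexpected' applies in the definition?** The Adverse events section gives none and does not point to the later one. The only explanation in the document is in the sponsor rule, "an event that is not listed in the protocol as an expected occurrence". No list of expected occurrences appears in the text shown.

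**Step 4: follow one event through.** Take an event with a serious outcome that the reporter regards as a known complication and that is on no protocol list.

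| | Ordinary meaning of 'unexpected' | Sponsor-rule meaning read back into the definition | Definition without 'and unexpected' |
|---|---|---|---|
| Is it an SAE? | No | Yes | Yes |
| Is the 24-hour form due? | No | Yes | Yes |
| Is it recorded and sent to the trial management committee? | Yes, no time limit | Yes | Yes |

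The first two columns differ only in how the reporter reads one undefined word. The third gives the same answer whichever reading is taken.

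**The case against.** The strongest reply is that the definition excludes almost nothing. The section opens by saying "No significant adverse events are expected", and the only meaning the protocol gives to unexpected is absence from a protocol list. Read together, and with no list in the text shown, any serious event is unexpected and the 24-hour form is due. This is a fair reading and it limits the practical effect. It does not remove the conflict: the definition does not refer to that meaning, so the reporter must choose, and the later test remains redundant.

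A second reply is that no event disappears. This stands in full. Every AE, expected or not, must be recorded and must reach the committee through the Chief Investigator. At worst, what is lost is the SAE label, the form and the 24-hour limit.

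A reader might infer more than this, and the document does not support it:

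- *That the safety comparison between arms would be incomplete, or SAE counts by arm distorted.* Neither the objectives nor the listed outcomes include an adverse-event comparison, and AE recording does not depend on expectedness.
- *That the early-stopping rule is compromised.* The stopping section speaks of loss of equipoise or a major adverse effect of treatment. It uses neither the SAE label nor an SAE count, and the committee receives all adverse events in any case.
- *That sponsor reporting fails.* With one meaning of expected used throughout, an expected event does not go to the sponsor under the present wording, and would not after the correction.

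**Conclusion.** The contradiction is certain on the wording. One section makes expectedness a condition of being an SAE; another treats it as a separate test applied to SAEs. The consequence is narrow: on the literal reading, a serious event judged expected escapes the SAE form and its 24-hour limit, and follows the AE route, which has no time limit.

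The number of events affected cannot be derived from the protocol. It ranges from few or none, if the sponsor-rule meaning is read into the definition, up to every serious event that a reporter considers a known complication, if the ordinary meaning is used. The lower end assumes that the protocol contains no list of expected events, which is true of the text shown. The upper end assumes that reporters apply the definition as worded.

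The point is worth correcting because it concerns prompt notice of serious events and the remedy is very small. It is not a finding against any outcome, analysis or stopping decision in the plan.

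**What to change.** In the Adverse events section, delete the words 'and unexpected' from the SAE definition, so that seriousness alone triggers the 24-hour form. Leave relatedness and expectedness where they already serve a purpose, as the sponsor-reporting test in the Serious Adverse Events (SAE) section. That test needs no rewording.

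The cost is two words in the protocol and possibly a few more SAE forms. If site staff already treat every serious event as unexpected, practice does not change.
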